## **9. INFORMED CONSENT, ETHICAL REVIEW, AND REGULATORY CONSIDERATIONS**

### **9.1. Informed Consent**

Before any study-related screening procedures are undertaken and before any prohibited medications are withheld from the patient, patients will be given an IEC/IRB-approved ICD describing the study. The investigator or designee must ensure that each patient is informed of the goals, methods, expected benefits, and potential risks associated with participation in the study. Each patient must also be informed that participation is voluntary, and that they may withdraw from the study at any time. If the patient decides to participate, the ICD will be signed and dated by the patient, the person who obtained informed consent, and any other signatories required by local guidelines.

### **9.2. Ethical Review**

Prior to study initiation, the investigator at each study center must obtain approval from the IEC/IRB for the protocol, protocol changes, Investigator's Brochure, ICDs, and any other relevant documents (e.g., advertisements). The investigator will retain all written correspondence with the IEC/IRB.

During the study, the investigator will promptly notify the IEC/IRB of any changes that affect the conduct of the study and/or increase the risk to patients. SAEs and major protocol deviations that meet local reporting criteria will be communicated to the IEC/IRB as required. The IEC/IRB will be informed of any changes to the ICD or any other documents that had previously been approved, and may request their re-approval. The IEC/IRB will also be notified of study termination or completion.

### **9.3. Regulatory Considerations**

The study will be performed in accordance with the protocol, ICH guidances, the ethical principles of the Declaration of Helsinki, and all applicable local regulatory requirements and laws.

### **9.4. Protocol Compliance**

The clinical study will be conducted as described in the protocol.

Changes to the protocol will be approved by the sponsor and the IEC/IRB prior to implementation, unless the changes are necessary to eliminate immediate hazards to patients. In such a case, the investigator must notify the IEC/IRB in writing.

If changes to the protocol affect patients' informed consent (i.e., significant changes in study design or the risk associated with participation in the study), the ICD will be revised and resubmitted to the IEC/IRB. Once approved, the revised ICD must be signed by all new patients as well as all registered patients affected by the changes.

### **9.5. Confidentiality of Patient Information**

The investigator and designees will maintain the confidentiality of patient information throughout the study. Patient records or information may be viewed by monitors, auditors, IEC/IRB members, and regulatory authority representatives in order to review clinical study procedures and/or data, provided that patient confidentiality is maintained. Patient names or any identifiable variable will not be included in any reports, publications, or communications with the sponsor.

As this study involves sequencing of patient DNA, mutations in the genome of participating patients may be identified. All sequencing data collected in the course of this study will be anonymized and kept strictly confidential. Neither the patient nor the investigator will be notified of any DNA mutations identified. Study numbers will be used to correlate DNA results with study specific results without identifying any specific patient demographics.

### **9.6. Protocol Signatures**

Each Principal Investigator will sign the Principal Investigator protocol agreement ([Section 10](#)), and forward a copy to the sponsor or designee.

### **9.7. Final Report Signature**

For the clinical study report, the investigator who enrolled the most patients will be considered the coordinating investigator. If this is not possible, the sponsor will select the coordinating investigator.

The medical representative of the sponsor will sign the clinical study report to indicate that, to the best of his or her knowledge, the report accurately describes the conduct and results of the study.

## **APPENDICES**

**Appendix 1. Schedule of Events (Phase II)**

Day	Screening a		Cycle 1				Cycle 2			Cycles ≥3 s		Discontinuation t	30-Day Follow-up v	Q 3 Months Follow-up
	≤28		1 b	2	8	15	1	8	15	1	15			
	V1	V2												
Informed consent	X													
Enrollment c	X		X											
Demographics d	X													
Medical and oncology history e	X													
Weight and height f	X		X				X			X		X		
Pregnancy test g	X		X				X			X		X		
FSH and estradiol h	X													
Tumor biopsy i		X						X						
Blood sample for molecular profile			X				X			X		X		
Physical exam j	X		X		X	X	X	X	X	X	X	X	X	
Vital Signs k	X		X		X	X	X	X	X	X	X	X	X	
12-Lead ECG l	X		X			X	X		X	X	X	X		
ECOG performance status m	X		X				X			X		X	X	
Hematology n	X		X		X	X	X	X	X	X	X	X	X	
Clinical chemistry o	X		X		X	X	X	X	X	X	X	X	X	
Urinalysis	X		X				X			X		X		
Concomitant medication review	X		X		X	X	X			X		X	X	
AK-01 dosing p			X				X			X				
PK sampling q			X	X	X	X						X		
AK-01 compliance					X	X	X			X		X		
AE monitoring	X	X	X	X	X	X	X	X	X	X	X	X	X	
Radiographic tumor assessment	X									X r		X u		
Survival assessment														X w

Abbreviations: AE – adverse event; CT – computed tomography; C – cycle; ECG – electrocardiogram; ECOG – Eastern Cooperative Oncology Group; EDC – electronic data capture; D – day; FSH – follicle stimulating hormone; hr – hour; ICD – informed consent documents; MRI – magnetic resonance imaging; PK – pharmacokinetic; RECIST – Response Evaluable Criteria in Solid Tumors; V – visit; Q 3 months – every 3 months

- a. All screening procedures must be performed within 28 days prior to Cycle 1 Day 1 (C1D1). Patients will undergo preliminary screening procedures at Visit 1 (V1) before becoming eligible for pre-treatment tumor biopsy (V2).
- b. Day 1 will be the day of receipt of the first dose of AK-01 in cycle 1, which will be administered in the clinic. Day 1 must be confirmed prior to dosing. Each visit in the cycle will occur +/- 2 days from the scheduled date. Procedures scheduled for Days 1, 8, and 15 of a cycle may be performed up to 2 days prior to dosing, but not following dosing (with the exception of PK sampling and ECG recording, see schedule). The patient must stay on the cycle schedules despite dose interruptions.
- c. A patient is considered entered in the study from the time the ICD is signed. A unique study number is assigned to each patient at this time. Between completion of screening and the first dose of IMP, a dose cohort will be assigned. A patient is considered enrolled in the study once a cohort has been assigned.
- d. The sex assigned at birth, birth date (month and year), and race will be recorded for each patient. Historical and current use of alcohol and tobacco products will also be recorded.
- e. Medical and oncology history will be reviewed at the Screening visit. This review will include documentation of any clinically significant medical condition, the presence and severity of any symptoms/conditions associated with locally advanced or metastatic tumors, and detailed oncology history (tumor type, stage of disease at diagnosis, stage of disease at study enrollment, duration of malignancy, presence and site of metastatic disease, surgical history, and history of anti-cancer therapies).
- f. Patients will wear lightweight clothing and no shoes during weighing. Height will only be measured at the Screening visit.
- g. Female patients capable of childbearing will be required to use 2 birth control methods while on study and for up to 3 months after IMP discontinuation; sexually active male patients must use a barrier method of contraception (condom) during the study and for at least 90 days following the last dose of IMP. For all female patients, the investigator will document potential childbearing status. A pregnancy test will be done at screening, and must be negative for enrollment. Subsequently, pregnancy tests will be done for all patients of childbearing potential as indicated in the schedule; the results must be confirmed negative prior to dosing on Day 1 of each cycle. Pregnancy tests may use serum or urine; any positive urine pregnancy result will be confirmed with a serum pregnancy test. Any female patient or female partner of a male patient participating in this study must inform the investigator immediately if pregnancy is suspected. Pregnancy testing is not required after the Screening visit for female patients without childbearing potential (documented history of tubal ligation, bilateral oophorectomy or hysterectomy, or post-menopausal for at least 1 year with confirmatory FSH and estradiol results).
- h. For women who are post-menopausal, a confirmatory test of serum FSH and estradiol levels will be done at screening.
- i. In Phase II, collection of a pre-treatment tumor biopsy (or archived tissue, as described above) is mandatory for all patients (SCLC patients tumor biopsies will be required unless the primary or metastatic tumor site is inaccessible or a quality biopsy

- cannot be obtained). Anticoagulants, antiplatelets, and nonsteroidal anti-inflammatory drugs should be stopped prior to tumor biopsy according to institutional practice.
- j. Following the first administration of AK-01, the physical exam will be symptom-directed and at the discretion of the investigator. After ICD signature, any clinically significant change in physical exam from baseline will be recorded as an AE.
  - k. Vital sign assessments will include sitting blood pressure, pulse and body temperature. Additional vital sign assessments may be performed as clinically indicated. For visits in which both vital signs and blood samples are collected, vital signs will be obtained prior to blood collection. Any clinically significant result of vital sign assessment will be documented as an AE.
  - l. Each ECG will be a triplicate assessment. In Cycle 1, ECGs will be performed at the following time points relative to the first dose on Day 1 and Day 15: 0 hours (pre-dose) and 1, 2, 4, 6, and 8-12 hours post-dose. ECGs will be performed predose on Day 1 and Day 15 in subsequent cycles. An ECG will also be performed prior to any inpatient dose escalation, and at any point the investigator considers it is clinically indicated. For visits in which both ECG and vital signs are collected, vital signs will be measured prior to ECG. An ECHO evaluation may be performed if clinically indicated.
  - m. ECOG status will be assessed according to the criteria in Appendix 4.
  - n. Refer to Appendix 2 for a list of hematology assessments. Additional hematology assessments may be conducted if deemed necessary by the investigator
  - o. Refer to Appendix 2 for a list of clinical chemistry assessments. Additional clinical chemistry assessments may be conducted if deemed necessary by the investigator
  - p. Patients will be dispensed AK-01 capsules on Day 1 for all cycles of Phase II. AK-01 may be dispensed up to 2 days prior to each scheduled dispensing day to facilitate patient scheduling. All assessments on the day of dosing will be performed prior to the first administration of AK-01, unless noted otherwise. Patient safety and toxicity will be evaluated prior to each dose, and patients will only be dosed if the results of safety assessments are deemed acceptable by the investigator. AK-01 will be taken orally twice daily approximately 12 hours apart (see [Section 5.2](#)). Patients will be encouraged to fast for 1 hour prior and following AK-01 dosing. Patients will self-administer the dose when not in the clinic, but on scheduled visit days the first dose of the day will be administered in the clinic after study procedures are completed. Patients will be dosed in cycles of 21 days at the dose assigned by the sponsor, unless the dose has been reduced for toxicity. Delays in the administration of AK-01 will be managed by the investigator on a case-by-case basis.
  - q. PK sampling will be performed in Cycle 1 of both Phase I and II at the following time points relative to the first dose on Day 1 and Day 15: 0 hours (pre-dose) and 1, 2, 4, 6, and 8-12 hours post-dose. Additional trough samples will be obtained prior to dosing on Day 2 and Day 8 of Cycle 1. The sampling schedule may be modified following review of PK data from the first cohort in Phase I to optimize collection times. A PK sample will also be obtained at the Discontinuation visit. A maximum of 3

additional PK samples may be drawn at other time points during the study, if warranted and agreed upon by both the investigator and the sponsor.

- r. A CT scan with IV contrast and assessment of tumor response by RECIST (v. 1.1, see Appendix 10) will occur within 1 week of the last dose of Cycle 2 and Cycle 4, and every 9 weeks ( $\pm$  1 week) thereafter for the duration of treatment. The schedule of tumor assessments will be maintained independent of any treatment schedule delays or changes. All CT scans will include the chest, abdomen and pelvis. For each tumor assessment, the date, method, and response evaluation will be recorded. Tumor response will not be evaluated at the screening CT scan (collected as the baseline). MRI may be performed instead of CT if a patient cannot tolerate CT contrast agents due to an iodine allergy. An individual patient will be monitored by the same methodology throughout the study. For patients that meet RECIST criteria for complete response or partial response, a confirmatory radiographic assessment will be obtained 4 weeks (+/- 5 days) after the response criteria was met.
- s. Dosing of AK-01 may continue until disease progression if the patient is receiving benefit and is experiencing no severe toxicity in the opinion of the investigator. Following Cycle 1, an entire cycle may be delayed or advanced by +/-1 day for administrative reasons, in which case it will be shortened (or lengthened) by 1 day, respectively.
- t. The discontinuation date will be recorded with the primary reason for discontinuation (if applicable). The patient will attend a Discontinuation visit as soon as possible after participation ceases.
- u. A CT scan and assessment of tumor response will be performed at the Discontinuation visit for patients who discontinue the study for reasons other than radiographic progression, and if a CT scan has not been performed within the prior 4 weeks.
- v. Patients will attend a follow-up visit 30 days (+/- 7 days) following the last dose of IMP.
- w. Patient survival will be confirmed approximately every 3 months for up to 1 year.

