### 3.3.2. Dose Modifications for Toxicity

Dose modifications are permitted as described below for toxicities that emerge throughout the study.

IMP may be withheld for up to 21 days to allow sufficient time for recovery from toxicity, but patients who do not recover within this period will be withdrawn. Following recovery, IMP may be resumed at the same dose or at a reduced dosing frequency, depending on the type and severity of toxicity experienced (see [Table 1](#)).

[Table 1](#) describes AK-01 dose modifications for patients who experience toxicity.

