### 5.2.2. Dose and Regimen

AK-01 will be administered twice daily, every day of a 21-day cycle. Patients will be dosed continuously: there will be no dosing holiday between cycles.

In Phase I, the dose of AK-01 will be between 25-75 mg BID per day (see [Table 3](#)). Patients in the first cohort of Phase I will receive 25 mg BID AK-01. Following a review of safety and other relevant data from this cohort, the SAC will decide on the dose for the subsequent cohort based on [Table 3](#). Following DLT or completion of Cycle 1, dosing for a given patient will be based on individual safety and tolerability.

For Phase II, the sponsor and SAC has established the dose of AK-01 as 25mg BID.

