### Progression Free Survival

Progression free survival (PFS) is defined as the time from the date of first study drug treatment until the date of radiographic documentation of disease progression (as defined by RECIST v 1.1) or death due to any cause, whichever is earlier. Patients without progressive disease or death will be censored at the date of the last adequate tumor assessment. Patients with disease progression or death after missing (or not evaluable)  $\geq 2$  consecutive post baseline tumor assessments will be censored at the date of the last adequate tumor assessment before the missed (or not evaluable) tumor assessments. Technically, events after  $\geq 2$  missing assessments are identified as events that meet either of the following

- there was no preceding post-baseline adequate tumor assessment and the event occurred more than 1 week of the last dose in Cycle 4
- the first post-baseline assessment was performed within 1 week of the last dose in Cycle 2 and then the event occurred more than 10 weeks of the last dose in Cycle 4
- the event occurred more than 19 weeks (2x9 weeks + the allowed assessment window) after the last adequate tumor assessment.

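### The SAP's missed-scan rule for PFS counts from the last dose taken in Cycle 2 or 4, although the protocol keeps tumor scans on the calendar, so a dose hold can move or remove the censoring cut-off

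*Protocol*

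**What the plan says.** **Protocol.** Footnote r of the Phase II schedule (Appendix 1) says that CT scans "will occur within 1 week of the last dose of Cycle 2 and Cycle 4" and then follow at 9-week intervals with a one-week window, for as long as the patient is treated. It gives no study day for the first two. The same footnote adds: "The schedule of tumor assessments will be maintained independent of any treatment schedule delays or changes". Section 6.7.1 repeats that sentence. Footnote b says of the cycles themselves: "The patient must stay on the cycle schedules despite dose interruptions".

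On dosing, Section 5.2.2 states that "AK-01 will be administered twice daily, every day of a 21-day cycle", and Section 3.3.2 that "IMP may be withheld for up to 21 days to allow sufficient time for recovery from toxicity".

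**SAP.** Under Progression Free Survival in Section 6.1, an event that follows two or more consecutive missed or non-evaluable scans is censored at the last adequate assessment before the gap. Three alternative criteria then say how such events are found:

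1. "there was no preceding post-baseline adequate tumor assessment and the event occurred more than 1 week of the last dose in Cycle 4";
2. a pair of conditions that must both hold, one on the first scan ("the first post-baseline assessment was performed within 1 week of the last dose in Cycle 2") and one on the timing of the event ("then the event occurred more than 10 weeks of the last dose in Cycle 4");
3. the event came more than 19 weeks after the last adequate assessment.

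The first two depend on a dose date and the third does not. No nominal day is given, and nothing is said about a patient with no dose in Cycle 2 or Cycle 4. PFS is an exploratory Phase II endpoint (SAP 6.3), analyzed in the Efficacy Evaluable set (SAP 9.6.2).

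**The concern.** The rule is meant to detect missed scans, so its cut-offs should follow the dates on which scans were due. The protocol says those dates do not move with dosing. The last dose taken within a cycle does move: if a hold is running when the cycle ends, the last dose is earlier than the cycle end. The two clocks agree only when dosing is uninterrupted at the end of Cycles 2 and 4.

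Two errors can follow. A genuine progression on a scan done on its calendar date can be censored as though two scans had been missed. Conversely, an event that does follow two missed scans can be kept. Which happens depends on toxicity holds, so the handling of events is tied to tolerability.

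**Working it through.** **Inputs.** Cycles last 21 days with continuous dosing (Protocol 5.2.2). Study Day 1 is the Treatment start date (SAP 7.3). Holds last up to 21 days (Protocol 3.3.2) and do not shift the cycles (footnote b). Later scans are every 9 weeks, ± 1 week (footnote r). I ignore the one-day administrative shift of a cycle that footnote s permits.

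**Step 1: the SAP's own figures.** 2 × 9 + 1 = 19 weeks and 9 + 1 = 10 weeks, as stated or implied. With every dose taken, Cycle 2 ends on Day 2 × 21 = 42 and Cycle 4 on Day 4 × 21 = 84. Then:

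- Criterion 1 cut-off: 84 + 7 = Day 91.
- Criterion 2 cut-off: 84 + 70 = Day 154. This is the next scan date, 84 + 63 = Day 147, plus the 7-day window.

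Under uninterrupted dosing the cut-offs match the scan calendar.

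**Step 2: a hold running on Day 84.** Cycle 4 is Days 64 to 84. The last Cycle 4 dose and the two cut-offs (last dose + 7, last dose + 70) become:

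| Hold length | Last Cycle 4 dose | Criterion 1 | Criterion 2 |
|---|---|---|---|
| none | Day 84 | Day 91 | Day 154 |
| 7 days | Days 77–83 | Days 84–90 | Days 147–153 |
| 14 days | Days 70–83 | Days 77–90 | Days 140–153 |
| 21 days | Days 64–83, or none | Days 71–90, or none | Days 134–153, or none |

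The entry of none arises when the hold covers Days 64 to 84 completely. A patient who stops before Cycle 4 is in the same position.

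**Step 3: an event wrongly censored.** Suppose there is no adequate Cycle 2 scan, a hold runs on Days 68–84 (17 days, so permitted), and progression is seen on the calendar scan at Day 84.

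- As written: last Cycle 4 dose Day 67; cut-off 67 + 7 = Day 74; 84 > 74, so the event is censored. Only the baseline scan is left as a censoring date, so the patient contributes essentially no follow-up.
- From the scheduled end of Cycle 4: cut-off Day 91; 84 ≤ 91, so the event counts. Only one scan was missed.

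A Day 84 scan is caught when last dose + 7 < 84, that is, last dose on Day 76 or earlier. That needs a hold covering at least Days 77–84, or 8 days.

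**Step 4: an event wrongly kept.** Suppose a hold runs on Days 23–42 (20 days), the last Cycle 2 dose is on Day 22, and the scan is done on Day 42. The scan is 42 − 22 = 20 days after the last dose, which exceeds one week, so criterion 2 cannot apply. Criterion 3 gives 42 + 19 × 7 = Day 175. If this patient is still on treatment and misses the Day 84 and Day 147 scans, an event on Days 155–175 is kept. With the calendar anchor (Day 154) it would be censored.

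**Step 5: which holds matter.** Only a hold that includes Day 42 or Day 84 moves an anchor. Assume one hold of L days whose first day is equally likely to be any of Days 2–84 (83 days). The share is 2L/83: 14/83 = 17% for 7 days, 28/83 = 34% for 14 days and 42/83 = 51% for 21 days. The documents give no hold frequency, so these are shares of holds, not of patients.

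**The case against.** The best reply is that the protocol already settles the matter. If cycles stay on the calendar and scans ignore delays, the last dose of Cycle 2 can be read as the scheduled end of that cycle, Day 42. This is a fair reading of footnote r, although the footnote does not state it. It means that one cannot assert that patients on hold are scanned earlier. A reader might go further and infer a bias in when response is detected, and so in ORR. The documents do not support that: the independence sentence points the other way, and no effect on the primary test has been shown.

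The same reading is harder to apply to the SAP. Its criteria are offered as the technical identification of events, they refer to doses, and they name no scheduled day. The governing sentence does still require two consecutive missed scans, but in Step 3 the criterion contradicts that sentence.

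It can also be said that Step 3 mixes clocks: if scans too followed doses, the scan was due by Day 74 and Day 84 was late. But the protocol expressly detaches scans from treatment delays, so the calendar governs the scan. The case does need both a missed Cycle 2 scan and a hold at the end of Cycle 4. The Efficacy Evaluable set also requires a post-baseline assessment, so criterion 1 will reach few patients.

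A second tempting inference concerns early stops. Take a patient scanned on Day 42 who stops in Cycle 3 and dies on Day 160. Criterion 3 keeps the death (160 < 175), whereas a Day 154 cut-off would censor it at Day 42. This is not evidence of error in the present rule. Footnote r schedules scans only during treatment, and footnote u asks for a discontinuation CT only if none was done in the preceding 4 weeks. No protocol scan need have been missed, and censoring a real death there would itself be hard to defend. What stands is narrower: without a Cycle 4 dose, criteria 1 and 2 have no cut-off, and the SAP does not say what to do.

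**Conclusion.** The point holds for the SAP. Criteria 1 and 2 rest on a date that moves with dose holds, while the scans they are meant to track do not. With cycles fixed to the calendar, the criterion 1 cut-off can fall from Day 91 to as early as Day 71, and criterion 2 from Day 154 to as early as Day 134; either can also be undefined. Criterion 3 is unaffected.

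The reach is limited. It covers the exploratory PFS analysis, in patients whose hold spans the end of Cycle 2 or Cycle 4 or who stop before Cycle 4. The number of such patients cannot be estimated from the documents. The primary ORR test is not shown to change. In the protocol, footnote r is ambiguous and can be reconciled; it does not establish that scans actually shift.

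The conclusion assumes that footnote b and the independence sentence govern cycle and scan dates.

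**What to change.** **SAP 6.1.** Replace the last dose in Cycle 2 and in Cycle 4 with the scheduled end of those 21-day cycles, counted from the Treatment start date: Study Days 42 and 84. The cut-offs become Study Day 91 for criterion 1 and Study Day 154 for criterion 2, identical to the present rule when no dose is missed. State that the rule applies only to scans the protocol scheduled for that patient, so that scans not due after treatment stopped are not counted as missed. Re-anchoring does not supply one thing that criterion 2 also lacks, an explicit condition that no adequate scan lies between the first scan and the event; that can be added in the same edit.

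**Protocol.** The sponsor should reconcile the two statements in footnote r with footnote b and Section 6.7.1 so that one clock applies to the scans. Which clock is the sponsor's decision; if it is not the cycle calendar, the SAP days must follow it.

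**Cost.** Wording in the SAP criteria and a clarification of one protocol footnote. The SAP change adds no scans or patients and does not touch the primary test. It should be made before database lock.
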